- 522 potential, at visit 1 and visit 5. For those of childbearing potentials the required use of
- 523 contraceptives will be discussed.
- 524
- 525 ● Urine samples
- 526 ○ Albumin/creatinine ratio by urine spot

527 8 Proceedings for Adverse Events

528 8.1 Definition of Adverse Events

529 8.1.1 Definition of Adverse Events

530 An Adverse Event (AE) is any untoward medical occurrence in a subject administered
531 Investigational Medicinal Products (IMP) and which does not necessarily have a causal
532 relationship with this product. An AE can be any unfavourable and unintended sign, abnormal
533 laboratory finding, symptom or disease temporally associated with the use of IMP, whether or
534 not related to the product.

535 8.1.2 Definition of Adverse Reactions

536 Each AE is to be classified by the investigator as related or not related to the IMP. An Adverse
537 Reaction (AR) is a noxious and unintended medical response to a medical product related to any
538 dose. For an AE to be an AR the suspected association between the product and the unwanted
539 medical condition should be at least a reasonable possibility.

540 8.1.3 Definition of Serious Adverse Events

541 Each AE is to be classified by the investigator as serious or non-serious. Seriousness is not
542 defined by a medical term; it is a result or an outcome. An AE is defined as a Serious Adverse
543 Event (SAE) if it:

- 544 ● results in death
- 545 ● is life-threatening
- 546 ● requires inpatient hospitalisation or prolongation of existing hospitalisation
- 547 ● results in persistent or significant disability/incapacity
- 548 ● results in a congenital anomaly/birth defect
- 549 ● Important medical events that may not result in death, be life-threatening, or require
- 550 hospitalisation may be considered an SAR when, based upon appropriate medical
- 551 judgement, they may jeopardise the patient and may require medical or surgical
- 552 intervention to prevent one of the outcomes listed in this definition

553 Medical and scientific judgement should be exercised in deciding whether expedited reporting is
554 appropriate in other situations, such as important medical events that may not be immediately
555 life-threatening or result in death or hospitalisation but may jeopardise the patient or may require
556 intervention to prevent one of the other outcomes listed in the definition above. These should also

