557 usually be considered serious. Examples of such events are intensive treatment in an emergency
558 room or at home for allergic bronchospasm; blood dyscrasias or convulsions that do not result in
559 hospitalisation; or development of drug dependency or drug abuse.

560 **8.1.4 Definition of Suspected Unexpected Serious Adverse Reactions**

561 Each SAE that is at least possibly related to IMP is to be classified by the investigator as
562 expected or unexpected. A SAE that is at least possibly related to IMP, and **unexpected**, is
563 defined as a Suspected Unexpected Serious Adverse Reaction (SUSAR). It is expected if it is
564 already known from earlier trials or is mentioned in relevant documents (SPC, summary of
565 product characteristics).

566 **8.2 Assessment of Adverse Events**

567 **8.2.1 Assessment of Intensity**

568 Each AE is to be classified by the investigator as mild, moderate or severe.

569 **Mild:** Acceptable. The subject is awareness of symptoms or signs, but they are easy tolerated.

570 **Moderate:** Disturbing. The AE is discomfort enough to interfere with usual daily activity.

571 **Severe:** Unacceptable. The subject is incapacity to work or to do usual daily activities.

572 **8.2.2 Assessment of Causality**

573 **Unlikely:** The event is most likely related to aetiology other than the IMP.

574 **Possible:** A causal relationship is conceivable and cannot be dismissed.

575 **Probably:** Good reason and sufficient documentation to assume a causal relationship.

576 **8.3 Methods for Eliciting Adverse Events**

577 All adverse effects regardless of relationship to study drug or protocol procedure will be recorded
578 in the adverse event CRF, including date and time of symptoms.

579 The Investigator should record the diagnosis, if available. If no diagnosis is available then the
580 Investigator should record each sign and symptom as Individual SAEs.

581 **8.4 Reporting of Adverse Events**

582 **8.4.1 Reporting of Adverse Events**

583 All AEs will be recorded on a separate AE form in the CRF.

Protocol No: *EudraCT nr 2010022695-31*

Date: *20110204*

Version: *7.5*

22(30)

584 **8.4.2 Reporting of Serious Adverse Events**

585 In addition will SAEs also be reported by the investigator to the sponsor on a separate SAE form
586 within 24 hours after the SAE have been communicated to the investigator. Follow-up
587 information describing the outcome of the SAE and action taken will be reported as soon as it is

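### Section 8.3 tells investigators to record undiagnosed signs and symptoms as SAEs, which contradicts the protocol's own AE and SAE definitions (8.1.1, 8.1.3)

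*Protocol*

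**What the plan says.** Section 8.3 (Methods for Eliciting Adverse Events) opens with a rule of general scope: "All adverse effects regardless of relationship to study drug or protocol procedure will be recorded" in the adverse event CRF. The next two sentences say how to enter an event: "The Investigator should record the diagnosis, if available. If no diagnosis is available then the" "Investigator should record each sign and symptom as Individual SAEs".

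Section 8.1.3 sets a different rule for what makes an event serious: "Each AE is to be classified by the investigator as serious or non-serious. Seriousness is not" "defined by a medical term; it is a result or an outcome. An AE is defined as a Serious Adverse" Event if it meets one of a list of criteria, such as death, threat to life, hospital admission or disability.

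Section 8.4.1 sends AEs to an AE form in the CRF. Section 8.4.2 adds a further duty for serious events only: "In addition will SAEs also be reported by the investigator to the sponsor on a separate SAE form", within 24 hours of the investigator learning of the event.

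**The concern.** The sentence in 8.3 makes the lack of a diagnosis decide whether an entry is an SAE. Section 8.1.3 makes the outcome decide. An investigator who meets a mild symptom of unknown cause therefore has two instructions that cannot both be followed.

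What is at stake is the safety record. SAE status brings a separate form and a 24-hour clock. For events judged at least possibly related to the trial drug, it also brings the expectedness assessment of 8.1.4 and, if the event is unexpected, the reporting in 8.4.3. If non-serious symptoms enter this stream, the SAE listing no longer means what 8.1.3 says it means. The trial has two centres, so there is also room for one site to follow 8.3 and the other 8.1.3.

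**Working it through.** The protocol gives no expected rate of AEs, SAEs or undiagnosed symptoms, so there is no figure to reproduce. The check sets the sections side by side and then reasons about direction.

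**1. Scope of the rule in 8.3.** The heading and the opening sentence concern all adverse effects. The only condition on the disputed sentence is that no diagnosis is available. Nothing in 8.3 restricts it to events already judged serious.

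**2. Comparison with the other sections.**

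| Section | What it implies for an undiagnosed sign or symptom |
|---|---|
| 8.1.1 | Signs, symptoms and abnormal laboratory findings fall within the AE definition, with no reference to seriousness |
| 8.1.3 | The investigator decides seriousness for every AE, by outcome; a missing diagnosis is not a criterion |
| 8.2.1 | An AE may be mild, with symptoms that are easily tolerated |
| 7.1.7 | A hypoglycaemic episode needs the AE and safety information forms only if it meets the criteria for a serious AE |
| 7.1.8, 7.3 | Clinically significant worsening or laboratory abnormality is reported as an AE |
| 8.5 | Non-serious AEs are expected to exist, since some may later become SAEs |
| 8.3 | Each one is recorded as an SAE |

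Section 8.3 stands alone against the rest.

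**3. Direction of the effect.** Take one undiagnosed episode with *k* signs or symptoms, of which *j* meet a criterion in 8.1.3, so 0 ≤ *j* ≤ *k*.

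- SAEs recorded under the literal wording of 8.3: *k*.
- SAEs recorded if each is entered as an AE and classified under 8.1.3: *j*.
- Excess: *k* − *j* ≥ 0.

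The excess is zero only when every sign or symptom in the episode is serious. Diagnosed events are treated alike under both readings. Summed over all episodes, the literal SAE count is therefore equal to or greater than the count under 8.1.3, never smaller.

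**4. What follows from SAE status.** Each excess SAE needs the separate form under 8.4.2. If it is judged at least possibly related, 8.1.4 requires an expectedness assessment. If it is unexpected, it meets the protocol's definition of a SUSAR. A symptom that is neither fatal nor life-threatening would then fall under the 15-day route in 8.4.3 and would also go to the principal investigators in trials with the product.

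**5. Size.** The total excess is the sum of *k* − *j* over undiagnosed episodes. The protocol gives neither the number of such episodes nor their symptoms, so no value can be calculated.

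**The case against.** The strongest reply is that this is an evident one-word slip which sites would read correctly. Section 8.1.3 requires a seriousness decision for every AE ("Each AE is to be classified by the investigator as serious or non-serious"), 8.4.1 and 8.4.2 keep the AE and SAE forms apart, and 8.5 presupposes AEs that are not serious. Much of this stands. A slip is the likeliest explanation, many sites would read AEs, and inflation occurs only where the sentence is followed literally. It does not remove the contradiction: the sentence is a direct recording instruction, and nothing in 8.3 narrows it.

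Three stronger readings are tempting, and the protocol does not support them.

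- *Unrelated important medical events could be missed.* A reader might infer this because 8.1.3 says that events not requiring "hospitalisation may be considered an SAR when, based upon appropriate medical" judgement they may put the patient at risk. SAR suggests a drug relation. But that bullet stands under the stem that defines an SAE, and the paragraph after the list restates the criterion with no causality condition and says such events should usually count as serious. SAR is not in the abbreviation list. The label is a clerical slip without practical effect.
- *The comparison of SAEs between arms would be distorted.* The protocol specifies no such comparison. Its listed adverse event endpoint (3.2) is hypoglycaemia, which has its own form and definitions in 7.1.7. Nor does the protocol say anything to show that undiagnosed symptoms would be more frequent in one arm.
- *A particular number of false SAEs can be stated.* Any such number would be assumed. One that added the same count to each arm would also show no shift between arms.

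**Conclusion.** The point holds as an internal contradiction in the safety-recording rules, of minor weight. As written, 8.3 conflicts with 8.1.1 and 8.1.3. Its literal application can only leave the SAE count unchanged or raise it, by an amount that the protocol does not allow to be derived. The practical consequence is possible over-reporting: unnecessary 24-hour forms and, for symptoms judged possibly related and unexpected, unnecessary SUSAR handling.

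The contradiction rests on the text alone. The consequence rests on one assumption, that at least some investigators follow the sentence as it stands. The primary endpoint and the sample size in 9.2 do not depend on it.

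**What to change.** In section 8.3, replace *Individual SAEs* with *individual AEs, each classified for seriousness under 8.1.3*. This brings the recording rule into line with the definitions and leaves 8.4.2 to apply only to events that meet the criteria. While the section is open, SAR in 8.1.3 can be changed to SAE as a clerical correction.

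The cost is one phrase, plus the optional single-word correction. No visit, assessment, endpoint or sample size changes. If recording has already begun under the present wording, SAE entries made without a diagnosis should be checked against 8.1.3.
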